# IRB#: 06-044 A(11)

- Baseline FDG-PET (dedicated study of the brain) must be performed within 2 weeks prior to treatment initiation. It also must be performed at least 28 days after discontinuation of prior therapy directed at VEGF/VEGFR such as bevacizumab (Avastin), VEGF-Trap, or AZD2171. Any questions regarding the definition of anti-VEGF/VEGFR therapy should be discussed with the PI or co-PI.
- There is no limitation on the number of prior relapses or prior therapies.
- Patients must agree to practice adequate contraception. Women of childbearing potential must have a negative B-HCG pregnancy test documented within 7 days prior to registration. Women must not be breast feeding.
- If cytoreductive surgery is planned for tumor recurrence at the time of enrollment, such patients are eligible for the surgical arm, taking perifosine for 5-10 days preoperatively and then continuing perifosine after recovering from the effects of surgery.
- Measurable disease is not required for eligibility in patients who recently underwent resection as long as the following conditions are met as applicable:
  - Progression of disease led to the surgery
  - Gliadel wafers were not placed during the most recent surgery
  - Neither convection enhanced delivery nor catheters for infusion of chemotherapy were used during the most recent surgery
  - Radioactive seeds were not placed during the most recent surgery
  - The histology of the most recent surgery documented recurrent/persistent/progressive malignant glioma

Note, however, that patients who are eligible for surgery because of progressive disease may be considered for the surgical arm.

• Any adult patient with a recurrent/progressive malignant glioma is eligible. Patients will be eligible if the original histology was low-grade glioma and a subsequent histological diagnosis of a high grade (malignant) glioma is made.

# 6.2 Subject Exclusion Criteria

- Patients must not be taking EIAEDs. If patients were previously on EIAEDs that have been discontinued, patients must have been off the agent for at least 2 weeks prior to registration.
- Patients must not have any significant medical illnesses or other history that in the investigator's opinion cannot be adequately controlled with appropriate therapy or would compromise the patient's ability to tolerate this therapy.
- Patients with a history of any other cancer (except non-melanoma skin cancer or carcinoma in-situ of the cervix), unless in complete remission and off of all therapy for that disease for a minimum of 3 years are ineligible.
- Patients must not have active infection or serious intercurrent medical illness.
- HIV-Positive patients receiving combination anti-retroviral therapy are excluded from the study due to possible retro-viral drug interactions.
- Patients must not have any disease that will obscure toxicity or dangerously alter drug metabolism.
- Surgical arm only: Patients must not have received prior therapy with signal transduction inhibitors (including but not limited to ZD1839/gefitinib/Iressa, OSI-774/erlotinib/Tarceva, rapamycin/sirolimus, CCI-779/temsirolimus, STI-571/imatinib/Gleevec, bevacizumab/Avastin, VEGF-Trap, AZD2171, sorafinib, sunitinib). Any questions about the eligibility based on prior treatments should be discussed with the PI or co-PI.

[figure not shown]
## 7.0 RECRUITMENT PLAN

Patients will be recruited from the neurology and neuro-surgery services at MSKCC. All patients will be seen by a neuro-oncology attending. All patients entered in the protocol will give written informed consent. There are no gender or racial restrictions.

## 8.1 PRETREATMENT EVALUATION

The following studies are required within two weeks prior to starting perifosine:

- Complete history and physical exam including neurologic exam and KPS.
- Height and weight.
- CBC including WBC differential and platelet count.

# IRB#: 06-044 A(11)

- Comprehensive chemistry panel.
- Uric Acid
- Contrast enhanced MRI (with MR Perfusion if possible) of the brain. The same type of scan, i.e., MRI or CT, should be used throughout the period of protocol treatment for tumor measurement. Patients unable to undergo an MRI will undergo contrast enhanced CT scans. It also must be performed at least 28 days after discontinuation of prior therapy directed at VEGF/VEGFR such as bevacizumab (Avastin), VEGF-Trap, or AZD2171. Any questions regarding the definition of anti-VEGF/VEGFR therapy should be discussed with the PI or co-PI.
- **Brain FDG-PET:** It also must be performed at least 28 days after discontinuation of prior therapy directed at VEGF/VEGFR such as bevacizumab (Avastin), VEGF-Trap, or AZD2171. Any questions regarding the definition of anti-VEGF/VEGFR therapy should be discussed with the PI or co-PI.
- All brain PET scans must be performed on MSKCC scanners for adequate ability to compare scans over time.
- For patients with histologically documented malignant gliomas who will receive perifosine for their 2nd or greater relapse, the date that the most recent therapy was started will be recorded and used to calculate the time to the prior relapse for comparison with time to progression on perifosine (intrapatient comparison).

## 9.1 TREATMENT/INTERVENTION PLAN

Dosing will be continuous, and for the purpose of this trial a cycle will be defined as 28 days.

## 9.2 Dosing

Perifosine will be given as a 600 mg loading dose on day 1. The loading dose will be divided into 4 equal doses of 150 mg each. The first 3 doses should be given with food in the adult day hospital to allow intravenous antiemetic prophylaxis, and 4th dose at bedtime at home. The interval between doses of perifosine should be no less than 4 hours. On day 2, patients will start the maintenance dose of 100 mg daily at bedtime at home.

## 9.3 Pharmacokinetics/drug concentration in tumor tissue (all patients)

In addition to baseline serum, all patients will have weekly serum drawn during weeks 2-4. Patients in surgical arm of the trial will have blood drawn at baseline and during surgery to determine the concentration of perifosine in serum at the time of surgery. Tissue will also be collected for determination of the concentration of perifosine in tumor tissue relative to simultaneously collected serum. The date and time of blood collection should be recorded. In addition, the date and time of the most recent dose of pre-surgical perifosine should be recorded.

# IRB#: 06-044 A(11)

## 9.4 Treatment modifications (all patients)

*For grade 1* perifosine related adverse events, treatment with perifosine will not be interrupted.

For grade 2 perifosine related adverse events

For nausea, vomiting and diarrhea, maintain dosing with symptomatic treatment. The dose of perifosine may be repeated if emesis occurs within 30 minutes of taking the tablet(s) OR all the tablets are seen in the emesis.

For persistent nausea, vomiting or diarrhea, or other persistent grade 2 adverse events despite symptomatic treatment, the daily dose will be reduced by 50 mg.

For grade 3 or 4 perifosine related adverse events

Hold perifosine and re-evaluate the patient at least weekly until toxicity improves to < grade 2 (grade 0 or 1).

If the toxicity resolves in 7 days or less, maintenance (daily) perifosine should be restarted but the daily dose will be reduced by 50 mg.

If the toxicity resolves in 8-14 days, the patient will take another loading dose before reinitiating daily maintenance but the load will by reduced by 200 mg to 400 mg and the maintenance will be reduced to 50 mg. The loading dose will be divided into 4 equal doses of 100 mg each. The first 3 doses should be given with food in the adult day hospital to allow intravenous antiemetic prophylaxis, and 4th dose at bedtime at home. The interval between doses of perifosine should be no less than 4 hours.

If toxicity does not resolve within 14 days, the patient will be withdrawn from the study.

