# IRB#: 06-044 A(11)

Other Names:	Octadecylphosphopiperidine (OPP), D-21266, KRX-0401				
Molecular Formula:	C25H52NO4P				
M.W.:	461.66 g/mol				
CAS No.:	157716-52-4				
How Supplied:	Perifosine is supplied as a film-coated tablet containing 50 mg of active ingredient.				
Storage:	Store closed containers at room temperature (20-25 $^{\circ}$ C). Perifosine is hygroscopic, so containers must be kept closed and dry. Perifosine tablets must be dispensed in the original container.				
Stability:	Stability testing program ongoing. Perifosine has a demonstrated shelf stability of at least 3 years.				
Route of Administration: Oral with meals unless otherwise specified.					
Potential Drug Interactions: None reported.					
Availability:	ifosine is an investigational agent supplied to estigators by AOI Pharmaceuticals.				
Agent Accountability	The Investigator, or a responsible party designated by the Investigator, must maintain a careful record of the inventory and disposition of all agents received from AOI Pharmaceuticals using the Drug Accountability Record Form.				

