## 9.6.1 Antiemetic prophylaxis

Patients are to be instructed that perifosine is to be taken with food. Patients will maintain a daily patient treatment diary to track when they take each dose of perifosine and return the diary to the clinic each week along with any remaining medication. The pills should remain intact and should not be split unless a gastrostomy tube is being used.

All patients should have antiemetic medications prescribed and administered as needed, and adjusted during the cycle at the discretion of the treating investigator.

Patients should receive an oral or IV prophylactic antiemetic regimen. The regimen to be used is at the discretion of the treating investigator.

Premedication with a 5HT3 blocker with dexamethasone is recommended.

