#### 13.1 CRITERIA FOR REMOVAL FROM STUDY

All patients may continue therapy unless disease progression, death, or dose limiting toxicity is documented. The cause of death should be recorded.

The following events may be considered sufficient reason for discontinuing treatment with the study medication

- Serious toxicity due to the study drug graded according to the NCI Common Terminology Criteria for Adverse Events v3.0 [22]
- Conditions requiring therapeutic intervention not permitted by the protocol
- Unacceptable toxicity in the opinion of the patient or investigator even if not specifically defined elsewhere
- Personal preference by the patient for any reason
- Subject non-compliance with the defined treatment plan
- Medical or psychiatric illness or social environment which in the investigator's judgment renders the patient incapable of further therapy.
- Any other situation where, in the opinion of the investigator, continued participation in the study would not be in the best interest of the patient
- Treatment delay due to toxicity greater than 14 days
- Pregnancy
- Disease progression

All reasons for discontinuation of treatment must be documented in the flow sheets.

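### Section 9.4's dose-reduction and restart rules work from 100 mg daily but not for a patient already on 50 mg, where quicker recovery leads to 0 mg and slower recovery to a 400 mg reload

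*Combined protocol and SAP*

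**What the plan says.** Treatment starts with a 600 mg load in four doses. Then, in Section 9.2, "On day 2, patients will start the maintenance dose of 100 mg daily at bedtime at home".

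Section 9.4 sets the later changes:

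- **Grade 2:** for persistent nausea, vomiting or diarrhea, or "other persistent grade 2 adverse events despite symptomatic treatment, the daily dose will be reduced by 50 mg".
- **Related grade 3-4, resolved in 7 days or less:** "maintenance (daily) perifosine should be restarted but the daily dose will be reduced by 50 mg".
- **Related grade 3-4, resolved in 8-14 days:** another load is given before daily dosing resumes, but "the load will by reduced by 200 mg to 400 mg and the maintenance will be reduced to 50 mg".
- **Not resolved within 14 days:** withdrawal.

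On dose units, Section 5.0 states "Perifosine is supplied as a film-coated tablet containing 50 mg of active ingredient", and Section 9.6.1 states "The pills should remain intact and should not be split unless a gastrostomy tube is being used".

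On stopping, Section 4.2 continues treatment until toxicity, progression or death. Section 13.1 lets patients continue unless, among other things, dose limiting toxicity is documented, a term not defined for this trial. It then gives a list introduced by "The following events may be considered sufficient reason for discontinuing treatment with the study medication", which includes "Unacceptable toxicity in the opinion of the patient or investigator even if not specifically defined elsewhere".

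The readable text gives no lowest dose, no limit on reductions or reloads, and no separate rule for a patient on 50 mg. The perifosine dose footnote to the study calendar after Section 10.3 is cut off, so it could not be checked.

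**The concern.** Section 9.4 mixes a relative rule (subtract 50 mg) with a fixed one (reload 400 mg, maintain at 50 mg). They are consistent only from the starting dose. A patient reaches 50 mg by an ordinary route: one persistent grade 2 event, or one earlier grade 3-4 event resolving within 14 days. With 50 mg tablets normally kept whole, there is no lower daily step.

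From there the rules run backwards: slower recovery from severe toxicity brings a new load, and quicker recovery brings no drug. What is at stake is dosing safety. A long hold is a fair reason to reload, but 400 mg is sized for a patient coming down from 100 mg. Given to a patient whose severe toxicity arose on 50 mg, it may put more drug in the body than was there when the toxicity arose.

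**Working it through.** **Step 1. The plan's own figures, from the starting dose.** 600 - 200 = 400 mg; 400/4 = 100 mg per load dose; 100 - 50 = 50 mg daily. All agree with Section 9.4.

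**Step 2. The same rules by current dose.**

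| Event | On 100 mg daily | On 50 mg daily |
|---|---|---|
| Persistent grade 2 | 100 - 50 = 50 mg | 50 - 50 = 0 mg |
| Grade 3-4, 7 days or less | 100 - 50 = 50 mg | 50 - 50 = 0 mg, though told to restart |
| Grade 3-4, 8-14 days | 400 mg load, then 50 mg | 400 mg load, then 50 mg (maintenance unchanged) |

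For a patient on 50 mg, the drug given in the 28 days from restart is 0 mg in the 7-day branch and 400 + 27 x 50 = 1,750 mg in the 8-14 day branch. After an earlier 400 mg reload the load wording also splits: a cut of 200 mg gives 200 mg, while the stated target is still 400 mg.

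**Step 3. Amount in the body after the reload.** Inputs:

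- half-life t of 96-225 h (Section 3.5.1); Section 3.5 says it exceeds 100 h;
- four 100 mg doses, at least 4 h apart (Section 9.4) or 6 h apart (supportive care appendix);
- a hold of d = 8 or 14 days.

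Section 3.5.3 reports non-linear kinetics only for single doses above 300 mg, so 100 mg doses are treated as linear. Assumptions: one compartment, full absorption, steady state on daily dose D before the event.

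- Peak P = D/(1 - f), with f = 2^(-24/t); trough = P x f.
- Residual R = trough x 2^(-24d/t).
- After the load, A = R x g^3 + 100 x (1 + g + g^2 + g^3), with g = 2^(-h/t) and h = 4 or 6 hours.
- Ratio = A/P.

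| D | t (h) | P (mg) | A, 8-day hold | Ratio | A, 14-day hold | Ratio |
|---|---|---|---|---|---|---|
| 50 | 96 | 314 | 433-444 | 1.38-1.41 | 396-405 | 1.26-1.29 |
| 50 | 100 | 326 | 441-451 | 1.35-1.38 | 400-409 | 1.23-1.25 |
| 50 | 225 | 702 | 730-740 | 1.04-1.06 | 608-616 | 0.87-0.88 |
| 100 | 100 | 653 | 505-518 | 0.77-0.79 | 424-433 | 0.65-0.66 |

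From 50 mg, the ratio with an 8-day hold is above 1 throughout 96-225 h. With a 14-day hold it is above 1 only below about 150 h (it crosses 1 at 143-149 h, depending on dose spacing). From 100 mg it is 0.57-0.80 over the whole range. The minimum falls inside the range, near 170 h with a 14-day hold.

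**Step 4. Relaxing steady state.** Suppose the patient was at steady state on 100 mg and stepped down to 50 mg s days before the event, without a hold. The peak is then P x (1 + f^s), with P the 50 mg value. For s = 7 and t = 100 h this is 326 x 1.312 = 428 mg, and the ratio is 0.95-1.10. At 150 h it is 0.73-0.91, and at 225 h it is 0.66-0.85. At 225 h it is still below 1 with s = 28.

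**The case against.** The strongest reply is that the 8-14 day sentence describes a step down from 600/100 mg. A patient on 50 mg cannot be reduced to 50 mg, so the sentence may be silent there rather than a direction to reload. Likewise, the text never says that the 7-day branch stops treatment; that is inferred from 50 - 50 = 0. Sections 4.2 and 13.1 also allow treatment to stop. This much stands: the contrast sets a literal reading of one branch against an inferred outcome of the other, and an investigator is not compelled to reload. But the stopping text is discretionary or rests on an undefined term, whereas Section 9.4 is worded as a direction, and a clinician who follows it exactly will reload.

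The pharmacokinetic argument is also open to challenge. A half-life of 100 h is near the unfavourable end, steady state on 50 mg may not have been reached, and the post-reload amount at 100 h (400-451 mg) stays below the 653 mg peak on 100 mg daily. The first three reload doses are given in the day hospital so that intravenous antiemetics can be used. In Table 6, the three patients at 400/50 mg show only grade 1 nausea and diarrhea, though that is a small group and not one re-challenged after severe toxicity. These points stand. A reader might infer that the reload always raises exposure above the toxic level; Steps 3 and 4 do not support that.

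A reader might also infer that Section 9.4 fails at every dose but 100 mg. It does not: the grade 1 rule, symptomatic treatment of grade 2 events and withdrawal after 14 days work at any dose.

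**Conclusion.** The point holds for further dose reductions from 50 mg. The core of it, 0 mg in one branch against a 400 mg reload with unchanged maintenance in the other, is plain arithmetic and needs no model. That the reload may exceed the earlier peak does depend on the model: 0.87-1.41 times from steady state on 50 mg, governed by half-life and length of hold, and often below 1 after a recent step-down. From 100 mg the reload is a real reduction.

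The documents give no rate of recurrent toxicity, so the number affected is unknown, but it is probably small. The patient must be on 50 mg, have a related grade 3-4 event, and recover in days 8-14. Section 3.5.2 puts resolution of chronic nausea at about 48 hours. It also says fatigue may persist for weeks, so recovery in days 8-14 is plausible for some.

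A reader might infer that the 6-month progression-free survival result is compromised. Nothing supports that: the Biostatistics section (14.0) counts progression or death due to disease, and the two-stage design is untouched. The conclusion that no rule exists is subject to the cut-off calendar footnote.

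**What to change.** Add to Section 9.4:

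- 50 mg daily is the lowest dose.
- The 400 mg reload applies only to a patient who was on 100 mg or more when the event began. The words ‘or more’ cover the higher dose that Section 9.6.8 may allow after an unavoidable switch to an enzyme-inducing antiepileptic.
- A patient on 50 mg who needs a further reduction, for a related grade 3-4 event or for persistent grade 2 toxicity despite symptomatic treatment, gets no reload and discontinues perifosine. Follow-up for progression and survival continues.

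Restarting 50 mg without a load would also be workable. Discontinuation is preferred because it is what subtracting 50 mg already implies.

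The cost is a few sentences in an amendment, with no change to sample size or the primary analysis plan. The downside is that a few patients stop earlier than the present text would have them do. Because time to treatment failure (Section 12.0) counts early discontinuation, their event on that measure would also come earlier.

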## 9.5 Treatment Schedule for patients participating in the Pre-operative study:

Patients who are candidates for surgical resection of recurrent disease will be considered for a pre-operative study to evaluate biological/tissue correlates. Patients who choose to participate in this component of the study must have a brain MRI (with MR Perfusion if possible) performed within 14 days of taking pre-operative perifosine. Patients unable to undergo MRI will have CT scans. A brain FDG-PET scan must also be performed within 14 days of taking preoperative perifosine. The drug will be administered for 5-10 days prior to the

# IRB#: 06-044 A(11)

surgery. The last dose will be given the night before surgery. Patients on the surgical arm will also undergo a pre-operative FDG-PET following at least 5 days of perifosine and before surgery to correlate metabolic and tissue effects during treatment.

Day of Surgery: Prior to the surgical procedure, tissue freezer vials should be labeled with the patient's protocol study identifier number(s). Additionally, a thermos with liquid nitrogen (preferably), or if not possible, an ice bucket with dry ice should be prepared. All attempts will be made to obtain specimens immediately adjacent to the areas of resection taken for "permanent sections" in order to optimize the likelihood that the tumor seen on permanent sections is representative of that taken for analysis. Once the pathologist has made a diagnosis of "tumor" on frozen section at the time of surgical resection, the tumor tissue should be divided into 50 - 100mg pieces.

At the time of surgery 10ml of blood will be collected for pharmacodynamic analysis.

Following surgery: A post-operative MRI/CT scan should be done no later than 96 hours from surgery. Once patients have recovered from the effects of surgery and demonstrated wound healing, they will restart perifosine (load and maintenance). Patients are not required to have residual disease to continue perifosine. Treatment with perifosine post-operatively should start a minimum of 7 days after surgery. If more than 14 days have passed since the post-operative MRI was performed, new baseline brain MRI (with MR Perfusion if possible) and brain FDG-PET sans must be performed.

## 9.6 Supportive Care Guidelines (all patients)

[figure not shown]
## 9.6.1 Antiemetic prophylaxis

Patients are to be instructed that perifosine is to be taken with food. Patients will maintain a daily patient treatment diary to track when they take each dose of perifosine and return the diary to the clinic each week along with any remaining medication. The pills should remain intact and should not be split unless a gastrostomy tube is being used.

All patients should have antiemetic medications prescribed and administered as needed, and adjusted during the cycle at the discretion of the treating investigator.

Patients should receive an oral or IV prophylactic antiemetic regimen. The regimen to be used is at the discretion of the treating investigator.

Premedication with a 5HT3 blocker with dexamethasone is recommended.

#### 9.6.2 Diarrhea Management

All patients should be instructed to take loperamide at the earliest signs of diarrhea and/or abdominal cramping after beginning study medication. This can include (a) loose stool, (b) the occurrence of 1 to 2 more bowel movements than usual in 1 day, or (c) an unusually high volume of stool.

Loperamide should be dosed in the following manner: 4 mg at the first onset of diarrhea, then 2 mg every 2 hours around the clock until diarrhea free for at least 12 hours. Patients may take 4 mg every 4 hours during the night.

Additional antidiarrheal measures may be used at the discretion of the treating physician as warranted by the patient's condition.

